6.5. Missing Data

All attempts will be made to collect all data per protocol. Any data point that appears to be erroneous or inexplicable based on clinical judgment will be investigated as a possible outlier. If data points are identified as outliers, sensitivity analyses may be performed to examine the impact of including or excluding the outliers. Any substantive differences in these analyses will be reported.

For time to event outcomes, subjects who are lost to follow-up or terminate the study prior to Day 29 and prior to observing/experiencing the event will be censored at the time of their last observed assessment. Subjects who die prior to observing/experiencing the event will be censored at Day 29.

For the analysis of the key secondary outcome, subjects who are discharged but are subsequently re-admitted prior to Day 15 without a reported clinical score, their clinical score will be imputed at 7, which is the highest value for a hospitalized subject.

For the analyses of the secondary outcomes that involve clinical score (i.e. the key secondary outcome and time to improvement), if a subject is discharged from the hospital (but not to hospice or other end-of-life care) without a previously or concurrently reported clinical score of 1 or 2, then their clinical score at the time of discharge will be imputed as 2, which is the highest value for a non-hospitalized subject. If a subject terminates early from the study while they are

hospitalized or completes the study while still hospitalized, the last observed clinical score assessment will be used as their final assessment.

For the modified version of the ordinal score described in Section 4.3, if a subject is discharged from the hospital without a previously or concurrently reported clinical score of 2 or 3, then their clinical score at the time of discharge will be imputed as 3, which is the highest value for a non-hospitalized subject.

For the analyses of the secondary outcomes described in Section 3.3, the following imputation rules will be used for subjects who are lost to follow-up, terminate early from the study, or do not have further outcome data available after discharge for any reason:

- NEWS Total score (any missing study day)
 - If the subject dies or is discharged to hospice or other end-of-life care prior to the missing study day, the worst NEWS score (20) will be imputed

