 - If the subject is discharged (not to hospice or other end-of-life care) prior to the missing study day, a NEWS score of 2 will be imputed.
 - If the subject is neither dead nor discharged, use the previous NEWS total score, or missing component-carried forward for all subsequent visits.
- Days of Non-invasive ventilation/high-flow oxygen:
 - If the subject's clinical status scale is 6 at the last observed assessment, then the subject will be considered to be on non-invasive ventilation/high-flow oxygen through Day 29. The endpoint will be total days when assessments are available plus all imputed days following the last observed assessment.
 - If the subject is not on non-invasive ventilation/high-flow oxygen at the last observed assessment, then the subject will be considered to not be on non- invasive ventilation/high-flow oxygen for the remainder of follow-up. Thus, no additional imputed days will be added to the number of days recorded on available assessments.
- Days of ventilation/ECMO:
 - If the subject's clinical status scale is 7 at the last observed assessment, then the subject will be considered to be on ventilation/ECMO through Day 29. The endpoint will be total days when assessments are available plus all imputed days following the last observed assessment.
 - If the subject is not on ventilation/ECMO at the last observed assessment, then the subject will be considered to not be on ventilation/ECMO through Day 29. Thus, no additional imputed days will be added to the number of days recorded on available assessments.
- Days of Oxygen:
 - If the subject's clinical status score is 5, 6, or 7 at the last observed assessment, then the subject will be considered to be on oxygen through Day 29. The endpoint will be total days when assessments are available plus all imputed days following the last observed assessment.

- If the subject is not on oxygen at the last observed assessment, then the subject will be considered to not be on oxygen through Day 29. Thus, no additional imputed days will be added to the number of days recorded on available assessments.
- Days of Hospitalization
 - If the subject is discharged and no further hospitalization data are available, then the subject will be assumed to not have been readmitted. Thus, no additional imputed days will be added to the number of days recorded on available assessments. If a subject dies while hospitalized, the number of days of hospitalization will be imputed as 28 days.

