8.2.2. NEWS

The median time to discharge or to a NEWS of ≤ 2 and CI will be summarized by treatment group ([Table 29](#)). The hazard ratio and log rank p-values will be provided with the summaries. Differences in time-to-event endpoints by treatment arm will be summarized with Kaplan-Meier curves. Number at risk, hazard ratio and log rank p-values will be included on the figures ([Figure 16](#)).

The mean, confidence interval, median, minimum, and maximum NEWS at Baseline and Study Visit (not necessarily actual) Days 3, 5, 8, 11, 15 and 29 will be presented by treatment arm as well as change from baseline at each post-Day 1 visit ([Table 31](#)). A figure with mean and confidence interval over time will also be presented by treatment arm ([Figure 18](#)).

Subject listings of NEWS responses (overall and individual components) by day will be generated ([Listing 6](#)).

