Table with similar format:

Table 28: Summary of Clinical Status Score by Treatment Group and Study Visit – mITT Population, Baseline Ordinal Score of 6

Table 29: Time to Discharge or to a NEWS of ≤ 2 by Treatment Group – Baseline Ordinal Score of 4 or 5

Analysis Population	Treatment Group	m	n	First Quartile Time (Days)		Median Time (Days)		Third Quartile Time (Days)		HR	
				Estimate	95% CI	Estimate	95% CI	Estimate	95% CI	Estimate	95% CI
mITT Population	Interferon beta-1a + RDV (N=X)	x	x	x.x	x.x, x.x	x.x	x.x, x.x	x.x	x.x, x.x	x.xx	x.xx, x.xx
	Placebo + RDV (N=X)	x	x	x.x	x.x, x.x	x.x	x.x, x.x	x.x	x.x, x.x		
As Treated Population	Interferon beta-1a + RDV (N=X)	x	x	x.x	x.x, x.x	x.x	x.x, x.x	x.x	x.x, x.x	x.xx	x.xx, x.xx
	Placebo + RDV (N=X)	x	x	x.x	x.x, x.x	x.x	x.x, x.x	x.x	x.x, x.x		

N= Number of subjects in the specified treatment group and analysis population.
m = Number of subjects had a NEWS of ≤ 2 at baseline.
n = Number of subjects who discharged or had a NEWS of ≤ 2 prior to Day 29.
HR is the ratio of the hazard of discharge or NEWS of ≤ 2 in each treatment group estimated from the Cox model. The ratio is Interferon beta-1a + RDV to Placebo + RDV.

Table with similar format:

Table 30: Time to Discharge or to a NEWS of ≤ 2 by Treatment Group – Baseline Ordinal Score of 6

Table 31: Summary of NEWS by Treatment Group and Study Visit – mITT Population, Baseline Ordinal Score of 4 or 5

Study Visit	Statistic	Interferon beta-1a + RDV (N=X)	Placebo + RDV (N=X)	Difference
Baseline	n	x	x	--
	Mean (95% CI)	x.x (x.x, x.x)	x.x (x.x, x.x)	x.x (x.x, x.x)
	Median	x.x	x.x	x.x (x.x, x.x)
	Range (Min, Max)	x, x	x, x	--
Day 3	n	x	x	--
	Mean (95% CI)	x.x (x.x, x.x)	x.x (x.x, x.x)	x.x (x.x, x.x)
	Median	x.x	x.x	x.x (x.x, x.x)
	Range (Min, Max)	x, x	x, x	--
	n ^a	x	x	--
	Change from Baseline Mean (95% CI)	x.x (x.x, x.x)	x.x (x.x, x.x)	x.x (x.x, x.x)
[Repeat for Study Visit Days 5, 8, 11, 15, 22, 29 and Change from Baseline at each]				
n = Number of subjects with an assessment at both baseline and the time point being summarized.				
n ^a = Number of subjects with an assessment at both baseline and the time point being summarized.				

Programming Notes:

Use imputed NEWS scores as defined in Section 6.5.

Table with similar format:

Table 32: Summary of NEWS by Treatment Group and Study Visit – mITT Population, Baseline Ordinal Score of 6

Table 33: Oxygen Use by Treatment Group – Baseline Ordinal Score of 4 or 5

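### NEWS change from baseline is compared between arms without baseline adjustment, and the fixed post-discharge score of 2 records some recovered score 4 patients as worse (low priority)

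*SAP*

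**What the plan says.** Change in NEWS from Day 1 is a named secondary objective (protocol Appendix C, section 3; SAP 3.1). SAP 8.2.2 summarises NEWS at each visit; the summaries "will be presented by treatment arm as well as change from baseline at each post-Day 1 visit". No model is named. In the Table 31 shell (baseline ordinal score 4 or 5) the row "Change from Baseline Mean (95% CI") has its Difference column filled in, with a 95% CI and no p-value. Table 32 repeats this for score 6. The programming note reads "Use imputed NEWS scores as defined in Section 6.5".

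SAP 6.5 applies its rules to subjects who are lost to follow-up, terminate early, or "do not have further outcome data available after discharge for any reason". The NEWS item is headed "NEWS Total score (any missing study day"). If the subject was "discharged (not to hospice or other end-of-life care) prior to the missing study day, a NEWS score of 2 will be imputed". After death or discharge to hospice or end-of-life care the value is 20. A patient still in hospital keeps the previous score.

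Protocol Appendix C, 8.1.2.3 has NEWS taken daily in hospital and on Days 15 and 29. Section 8.1.2.1 says it cannot be obtained by phone or telehealth. The SAP expects low baselines: 3.3.5 has a special rule for baseline NEWS of 2 or less, and a Table 29 footnote counts such patients ("m = Number of subjects had a NEWS of" 2 or less at baseline). SAP 6.4 plans covariate adjustment only for the primary and key secondary outcomes, and baseline NEWS is not among the covariates.

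**The concern.** Two separate things happen once a discharged patient's missing score becomes 2.

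First, follow-up no longer varies for that patient, so the change score is a function of baseline alone. Subtracting baseline then adds baseline noise to the arm comparison instead of removing it. The reported interval is wider than it need be, and a chance baseline difference reappears in the change difference with its sign reversed.

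Second, the constant ignores where the patient started. Someone admitted with NEWS 0 or 1 who goes home recovered is recorded as having deteriorated. SAP 3.3.5 handles low baselines in the time-to-event NEWS endpoint, but nothing equivalent applies to the change summary.

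At stake are the precision and face validity of one secondary summary. No primary or key secondary inference is affected.

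**Working it through.** **Inputs from the documents.** Total sample size: 831/0.90 = 923.3, which reproduces the stated figure of about 923; allocation is 1:1, so about 461.5 per arm. Table 31 excludes score 6, so its n is somewhat smaller. Imputed values are 2 and 20. In the NEWS table, supplemental oxygen scores 2. The documents give no NEWS mean, SD, effect size or discharge timing, so everything below about spread and discharge share is assumed.

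**1. Sign of the imputed change.** Imputed change = 2 − baseline:

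| Baseline NEWS | 0 | 1 | 2 | 3 | 4 |
|---|---|---|---|---|---|
| Recorded change | +2 | +1 | 0 | −1 | −2 |

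Baseline 0 or 1 is recorded as worse. A patient on oxygen scores at least 2, so this requires a patient off oxygen, that is ordinal score 4. Score 5 patients and Table 32 are not exposed to it.

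**2. How much chance imbalance is possible.** SE of the baseline difference = SD × √(2/461.5). For SD 1, 2 and 3 the 95% chance range (1.96 × SE) is ±0.13, ±0.26 and ±0.39 points.

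**3. How much of it reaches the change difference.** Let f be the share set to 2 (taken as unrelated to baseline), b the slope of observed follow-up NEWS on baseline, and D the baseline difference. With no treatment effect and no deaths:

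- visit-score difference: (1 − f)b × D
- change difference: [(1 − f)b − 1] × D = −[f + (1 − f)(1 − b)] × D

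With f = 0.7, b = 0.5: 0.7 + 0.3 × 0.5 = 0.85, so the change difference carries 85% of D and the visit-score difference 15%. For b from 0.3 to 0.7 the change share is 79–91% at f = 0.7 and 93–97% at f = 0.9. With SD 2 and D at the edge of its chance range, 0.85 × 0.26 = 0.22 points appear with no treatment effect. In simulation (462 per arm, 3,000 runs, no deaths) the slope of the arm difference on D was −0.84 to −0.96 for raw change and −0.02 to +0.01 after adjustment.

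**4. Precision.** Assume baseline mean 4, SD 2; patients still in hospital have mean 6, slope 0.5 on baseline and residual SD 2.5; discharged patients are set to 2 and deaths to 20. For 60% discharged, 2% dead and 38% in hospital:

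- Mean of Y = 0.6 × 2 + 0.02 × 20 + 0.38 × 6 = 3.88
- In-hospital variance = 0.25 × 4 + 6.25 = 7.25
- Var(Y) = 0.6 × 4 + 0.02 × 400 + 0.38 × (36 + 7.25) − 3.88² = 11.78
- Cov(Y, baseline) = 0.38 × 0.5 × 4 = 0.76
- Var(change) = 11.78 + 4 − 1.52 = 14.26
- Residual variance after adjustment = 11.78 − 0.76²/4 = 11.64
- Change versus adjusted = 14.26/11.64 = 1.23; visit score versus adjusted = 11.78/11.64 = 1.01

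The simulated columns use 900 patients with baseline mean 3.2, SD 2, under differing assumed follow-up scores.

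| Discharged, dead | Change/adjusted: formula | Change/adjusted: simulated | Visit score/adjusted: formula | Visit score/adjusted: simulated |
|---|---|---|---|---|
| 60%, 2% | 1.23 | 1.28–1.35 | 1.01 | 1.01–1.05 |
| 80%, 3% | 1.28 | 1.28–1.30 | 1.00 | 1.00–1.01 |
| 60%, 0% | 1.39 | 1.9–2.5 | 1.02 | 1.05–1.15 |

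A variance ratio of 1.28 to 1.35 means an interval √1.28 = 1.13 to √1.35 = 1.16 times as wide. A few deaths scored 20 dominate the variance, which is why the penalty shrinks when they are included.

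**5. Who is counted.** The Table 31 footnote defines n as subjects assessed at both baseline and the visit, while its note calls for imputed scores. The two give different denominators. The shell also lists Day 22, which 8.2.2 omits and for which the schedule has no vital signs once the patient is discharged.

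**The case against.** The strongest reply is that the useful contrast is already in the table. Table 31 shows the baseline difference and the between-arm difference in mean NEWS at each visit, with CIs. The visit-score difference does not subtract baseline, and step 4 shows it nearly as precise as the adjusted estimate. When most values are a constant, adjustment adds little to that row. This stands: the loss is confined to the change row, which is nevertheless the stated objective.

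Nor is the raw change difference biased. Under randomization it has the same expectation as the difference in mean scored NEWS, and its CI already reflects baseline variation. This also stands. Stratification by ordinal score limits imbalance between strata, though not NEWS imbalance within them.

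The value 2 matches the threshold of the time-to-event NEWS endpoint, where a recovered patient with a low baseline counts correctly as a success on discharge. That makes 2 a coherent choice, but it does not make a rise from 0 to 2 a real deterioration.

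A reader might infer that every discharged patient is set to 2, or that better observed scores are overwritten. The documents do not support either reading. Scores recorded at in-person or home visits on Days 15 and 29 are kept, hospice and end-of-life discharges get 20, and only missing days are filled. The lead-in to the 6.5 rules could even be read as narrower than any missing day.

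**Conclusion.** The point holds in limited form. The change row of Table 31 is an unadjusted comparison that passes most of any chance baseline NEWS imbalance into the arm difference. It is unbiased but less precise: variance about 1.3 times the adjusted estimate with a few percent of deaths, and more without deaths. These ratios rest on assumed baseline spread, discharge share, death share and in-hospital follow-up scores.

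The wrong-sign change for baseline 0 or 1 follows directly from the rule and needs no assumption, but it is confined to ordinal score 4. A reader might try to attach a frequency from an assumed NEWS distribution. A normal curve with mean 3.2 and SD 2 puts about 20% of patients at 0 or 1, but it ignores the 2-point oxygen floor for score 5. The documents give neither the score 4 share nor its NEWS distribution, so no frequency can be stated. Nor do they give discharge timing by which to say that most values are imputed by a given day.

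Priority is low: this is one of the other secondary endpoints, reported descriptively and without a p-value.

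**What to change.** - **SAP 8.2.2 and Tables 31 and 32:** report the between-arm difference at each visit, with 95% CI, from a linear model of NEWS on treatment, baseline NEWS and, for Table 31, baseline ordinal score. Keep the raw means and raw change as description.
- **SAP 6.5:** for a missing day after discharge other than to hospice or end-of-life care, impute the lower of 2 and the last observed NEWS, at least as a sensitivity analysis. The model alone does not cure the fixed 2.
- **Table 31 footnote and note:** state whether n counts observed assessments or includes imputed scores, and show the number imputed at each visit. Align the 6.5 lead-in with the any-missing-day heading, and decide whether Day 22 belongs in the table.

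The cost is SAP wording and one model per visit. No new data are needed.

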8.2.3. Days of Oxygenation

Duration of oxygenation use will be summarized in a table using medians and quartiles by treatment arm ([Table 33](#)). Analyses will be performed in the mITT and As Treated populations. Bee swarm plots of oxygen days by treatment arm will be generated, where subjects whose days are imputed to the maximum of 28 days due to death are grouped separately from subjects who do not die ([Figure 20](#)).

8.2.4. Incidence of New Oxygen use

The incidence and duration of new oxygen use will be analyzed by treatment arm. This will only include subjects in category 4 at randomization. New use will be identified by a post-randomization score of at least 5; the number of subjects reporting new use and the incidence rate (and CI) will be reported.

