5.6.2 Retention

Retention of subjects is critical to the success of the trial since the primary endpoint is measured through Day 29 (+ 6-day window) and every effort should be made to retain subjects in the study. As such, after hospital discharge, subjects will be reminded of subsequent study visits and every effort will be made to accommodate the subject's schedule to facilitate follow-up within the specified visit window. However, there are many circumstances that impact a site's ability to obtain outcome information after discharge. For example, given the clinical course of COVID-19, a subject may be readmitted to another hospital after discharge and therefore be unavailable at Day 15 or Day 22. Even if a study visit is missed or study product is discontinued, every effort should be made to keep subjects in the study to monitor for safety, mortality and ordinal scale at Day 29. Subjects should not be withdrawn from the study because a site is unable to contact them for a follow-up visit.

Another common lost-to-follow-up scenario during ACTT-1, involved subjects (or their LARs) asking that the study products and blood draws be discontinued due to terminal illness. These subjects should also be encouraged to remain in study for the final Day 29 ordinal scale determination by chart review or phone call. To facilitate retention, follow-up visits may be conducted by phone, home visit or remote telehealth procedure as per institutional standards if in-person visits at the clinical site on Days 15 and 29 are not feasible. Day 22 visit is by phone call or remote telehealth procedure.

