3.2. Endpoints

Primary Endpoint

Time to recovery, where recovery is defined as clinical status in states 1, 2, or 3 of the 8-point ordinal scale, through Day 29 (+6).

- Clinical status of a subject (8-point ordinal scale) is defined below:
 8. Death;
 7. Hospitalized, on invasive mechanical ventilation or ECMO;
 6. Hospitalized, on non-invasive ventilation or high flow oxygen devices;
 5. Hospitalized, requiring supplemental oxygen;
 4. Hospitalized, not requiring supplemental oxygen - requiring ongoing medical care (COVID-19 related or otherwise);
 3. Hospitalized, not requiring supplemental oxygen - no longer requiring ongoing medical care;
 2. Not hospitalized, but new or increased limitation on activities and/or requiring new or increased home oxygen;
 1. Not hospitalized, no limitations on activities

Secondary Endpoints

The key secondary endpoints are:

- Clinical status (8-point ordinal scale) on Day 15.
- Time to recovery, where recovery is defined as clinical status in states 1, 2, or 3 of the 8-point ordinal scale, through Day 29 (+6).

The other secondary endpoints are:

- Ordinal outcome assessed while hospitalized (Days 3, 5, 8, 11) and on Days 15, 22, and 29.
- NEWS assessed daily while hospitalized (Days 3, 5, 8, 11) and on Days 15 and 29.
- Days of supplemental oxygen (if applicable).
- Days of non-invasive ventilation/high-flow oxygen (if applicable).
- Days of invasive mechanical ventilation/ECMO (if applicable).
- Days of hospitalization.
- Date and cause of death (if applicable).
- D-dimer and CRP on Day 1, while hospitalized (Days 3, 5, 8, 11), and on Days 15 and 29.
- SAEs.
- Grade 3 and 4 adverse events

- WBC with differentials, hemoglobin, platelets, creatinine, total bilirubin, ALT, AST, INR, d-dimer, and CRP on Day 1; Days 3, 5, 8, and 11 (while hospitalized); and Days 15 and 29 (if attends in-person visit or still hospitalized).

Exploratory Endpoints (not described in this SAP)

- Qualitative and quantitative polymerase chain reaction PCR for SARS-CoV-2 in OP swab on Day 1; Days 3, 5, 8, and 11 (while hospitalized); and Days 15 and 29 (if attends in-person visit or still hospitalized).
- Deep sequencing of the SARS-CoV-2 virus for those subjects with sustained vial shedding
- Qualitative and quantitative PCR for SARS-CoV-2 in blood on Day 1; Days 3, 5, 8, and 11 (while hospitalized).

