3.3.8. Days of Oxygen

Oxygen days will be defined as the number of days where the clinical status score is equal to 5, 6, or 7. The Post-Discharge Supplemental Oxygen CRF question regarding days of oxygenation (including ECMO, invasive ventilation, non-invasive ventilation, high-flow oxygen devices, and all other oxygen delivery devices) will be used for any time period the subject is not hospitalized at the study hospital. The total number of days will be the sum of all reported days, regardless of whether the days occur consecutively or in disjoint intervals. See Section 6.5 for the plan for handling subjects who do not have data through Day 29 or die prior to Day 29.

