The original (as-classified by the site) ordinal scores will be used as the primary scoring method for analyses. The following modified ordinal scale will be used in sensitivity analysis of select outcomes:

8. Death;
7. Hospitalized, on invasive mechanical ventilation or ECMO;
6. Hospitalized, on non-invasive ventilation or high flow oxygen devices at oxygen flow rate greater than 15L/min;
5. Hospitalized, requiring supplemental oxygen or high flow oxygen devices at oxygen flow rate less than or equal to 15L/min;
4. Hospitalized, not requiring supplemental oxygen - requiring ongoing medical care (COVID-19 related or otherwise);
3. Hospitalized, not requiring supplemental oxygen - no longer requiring ongoing medical care;
2. Not hospitalized, but new or increased limitation on activities and/or requiring new or increased home oxygen;
1. Not hospitalized, no limitations on activities.

This scale will be denoted as the “Modified Oxygen Use” ordinal scale.

NEWS has demonstrated an ability to discriminate subjects at risk of poor outcomes. This score is based on 7 clinical parameters (see Section 8.1.2.3 in Appendix C of the study protocol). This should be evaluated at the first assessment of a given study day and prior to administration of study product. The 7 parameters can be obtained from the hospital chart using the last measurement prior to the time of assessment and a numeric score given for each parameter (e.g., a RR of 9 is one point, oxygen saturation of 92 is two points). This is recorded for the day obtained. i.e., on Day N, the Day N score is obtained and recorded as the Day N score.

Oxygenation, Non-invasive ventilation/high flow oxygen, Invasive Mechanical Ventilation / extracorporeal membrane oxygenation (ECMO), hospitalization and mortality will be assessed using results of the 8-point ordinal scale and post discharge eCRF questions.

Safety will be assessed by the following:

- Cumulative incidence of serious adverse events (SAEs) through 28 days of follow-up.
- Cumulative incidence of Grade 3 and 4 AEs.
- Discontinuation or temporary suspension of study product administration (for any reason).
- Changes in white cell count, hemoglobin, platelets, creatinine, total bilirubin, ALT, AST, and INR, d-dimer, C-reactive protein over time. Note D-dimer and CRP are not graded.

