8.2.6. Incidence of New Non-Invasive Ventilation/High-Flow Oxygen

The incidence and duration of new Non-Invasive Ventilation/High-Flow Oxygen use will be analyzed by treatment arm. This will only include subjects in category 4 or 5 at randomization. New use will be identified by a post-randomization score of 6. The number of subjects reporting new use and the incidence rate (and CI) will be reported.

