8.2.8. Incidence of New Invasive Mechanical Ventilation/ECMO

The incidence and duration of new Invasive Mechanical Ventilation/ECMO use will be analyzed by treatment arm. New use will be identified by a post-randomization score of 7. The number of subjects reporting new use and the incidence rate (and CI) will be reported.

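### The incidence rules for new oxygen, NIV/high-flow and ventilation use ordinal scores alone, in conflict with SAP 4.3 and the duration rules, so new home oxygen is missed and support given elsewhere can be

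*SAP*

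**What the plan says.** The secondary objectives in SAP 3.1 pair the incidence and the duration of new support, both through Day 29. The two halves are derived differently.

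Incidence is set in SAP 8.2. For oxygen (8.2.4, baseline category 4 only): "New use will be identified by a post-randomization score of at least 5". For NIV/high-flow (8.2.6, baseline 4 or 5): "New use will be identified by a post-randomization score of 6". For ventilation/ECMO (8.2.8): "New use will be identified by a post-randomization score of 7". None of the three mentions another source, and SAP 3.3 has no separate derivation for incidence.

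Days of support are set in SAP 3.3.6 to 3.3.8, which start from the ordinal score and add a second source. For oxygen, 3.3.8 invokes "The Post-Discharge Supplemental Oxygen CRF question regarding days of oxygenation" and says that it "will be used for any time period the subject is not hospitalized at the study hospital". Sections 3.3.6 and 3.3.7 do the same for NIV/high-flow and for ventilation/ECMO.

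SAP 4.3 speaks for all of these measures together: they "will be assessed using results of the 8-point ordinal scale and post discharge eCRF questions".

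**The concern.** One objective is read from two different sets of data. Category 2 of the scale is "Not hospitalized, but new or increased limitation on activities and/or requiring new or increased home oxygen", so a discharged patient on new home oxygen sits below every incidence threshold, although SAP 3.3.8 counts that patient's oxygen days. The protocol also foresees that "a subject may be readmitted to another hospital after discharge and therefore be unavailable at Day 15 or Day 22" (Appendix C, 5.6.2), which is a situation where a score may be lacking but the CRF is meant to apply.

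What is at stake is the accuracy of the reported incidence of new support, and its agreement with the days-of-support tables for the same patients. The two can be linked. The programming note to Table 33 restricts days on oxygen, among those not on oxygen at baseline, to subjects with new use. If the incidence flag is what defines new use there, a patient known only from the CRF drops out of the duration summary too.

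**Working it through.** The documents state no incidence, power or sample size for these endpoints, so there is no figure to reproduce. The check sets the rules side by side and follows patients through them.

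| Support | Flag for new use (SAP 8.2) | Source for days (SAP 3.3) |
|---|---|---|
| Oxygen | score of 5 or more | scores 5 to 7, plus CRF |
| NIV/high-flow | score 6 | score 6, plus CRF |
| Ventilation/ECMO | score 7 | score 7, plus CRF |

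**When scores exist.** In hospital they are daily and record the worst status of the previous day (protocol Appendix C, 8.1.2.2). After discharge they are due on Days 15, 22 and 29, so if taken on those days they describe Days 14, 21 and 28. Appendix C, 7.4 also asks for daily scores on every readmission.

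**Patient 1: home oxygen.** Baseline 4, scored 4 throughout the stay, discharged on new home oxygen. Every score after discharge is 2. Under 8.2.4, 2 < 5, so no new use is recorded. Under 3.3.8 the CRF oxygen days are counted. The score cannot recover the event, because category 2 also covers activity limitation without oxygen. This miss needs no assumption about readmission or visit timing.

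**Patient 2: ventilated elsewhere.** Discharged, readmitted to a non-study hospital on Day 17, ventilated on Days 18, 19 and 20.
- With no daily readmission score, the scores describe Days 14, 21 and 28. None falls on Days 18 to 20, so 8.2.8 records no new ventilation, while 3.3.7 counts 3 days from the CRF.
- With daily readmission scores as 7.4 asks, a 7 is recorded and the event is counted.
- If the patient dies on Day 21 without a readmission score, the day-after-death assessment gives 8, which is not the 7 that 8.2.8 requires.

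The SAP itself allows for absent readmission scores. Section 6.5 imputes a 7 for a patient readmitted before Day 15 without a reported score, but only for the key secondary outcome, not for incidence.

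**Size.** Counted incidence = true incidence × (1 − s), where s is the share of new users whose only use goes unscored. Neither input is in the documents. On assumed values:

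| Assumed true incidence | Shortfall at s = 5% | Shortfall at s = 20% |
|---|---|---|
| 10% | 0.5 points | 2 points |
| 20% | 1 point | 4 points |
| 40% | 2 points | 8 points |

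This shows how the shortfall scales. It does not estimate it.

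**The case against.** The strongest reply is that SAP 4.3 already names both sources, so the plan intends to use the CRF and 8.2 is merely loosely worded. That shows intent, and it rules out saying that the plan discards the data. It does not settle what is programmed: 8.2.4, 8.2.6 and 8.2.8 are the specific rules for these endpoints, and each says how new use is identified.

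A reader might infer that all support at other hospitals is lost. The documents do not support that. Appendix C, 7.4 requires daily scores on all readmissions, and a score at Day 15, 22 or 29 can catch some support. How far daily scoring reaches non-study hospitals depends on the MOP, which is not among these documents.

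The home-oxygen case is narrow, since in-hospital scores record the worst status of each day and any oxygen need before discharge is already counted. That stands: the case is confined to baseline-4 patients never scored 5 or higher. Patient 2's death would be an event in the SAP 9.4 analysis of death or progression to invasive ventilation. That also stands, but it does not repair 8.2.8.

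Finally, the CRF form is not in the documents. They show that it asks about days of each support, but not whether it records dates or separates new home oxygen from prior use. The fix has to respect this.

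**Conclusion.** The point holds as an internal conflict with a definite consequence. The score-only flags in 8.2.4, 8.2.6 and 8.2.8 disagree with 4.3 and with 3.3.6 to 3.3.8. As written, new home oxygen in a baseline-4 patient never scored 5 or higher is always missed. Support at a non-study hospital can be missed, when no daily readmission score is obtained and it falls between the scheduled scores or the visit is missed. The loss of such patients from the Table 33 duration summary is conditional on the incidence flag defining new use there.

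The under-count cannot be sized. No readmission rate, share treated elsewhere or expected number of events is given, and SAP 3.3.2 does not expect many subjects to worsen after discharge. A reader might infer a bias towards whichever arm discharges sooner, because more of its follow-up would lie outside daily scoring. The mechanism is possible, but nothing in the documents shows that it operates or how large it would be.

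These are non-key secondary endpoints, summarized as rates with confidence intervals outside the p-value gatekeeping of SAP 6.8. The primary and key secondary analyses are unaffected. The change is worth making because it is cheap, but it is not critical.

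**What to change.** In SAP 8.2.4, 8.2.6 and 8.2.8, define new use as a qualifying post-randomization score OR at least one day of that support on the Post-Discharge Supplemental Oxygen CRF. Count home oxygen only if new or increased from before COVID-19, where the CRF or the recorded chronic oxygen history allows this to be judged.

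Apply the same definition to the tables that have a new-use section: 33, 35, 36 and 38 to 41. Tables 34 and 37 have none. Extend it to the progression endpoints in SAP 9.4 only if the CRF gives dates, since those are time-to-event analyses.

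The cost is SAP wording and programming, because the SAP already plans to use these CRF data for duration. The small downside is that post-discharge CRF data may rest on patient report.
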